## 6. Study Outcomes:

### 6.1. Primary outcome:

Primary outcome is the presence of any complication which necessitates PICC removal. This includes mechanical, central line associated blood stream infections (CLABSI) and major life threatening complications.

- i) Mechanical complication will be considered present if there is a line infiltration, occlusion, phlebitis, and dislodgement, resulting in removal of PICC.
- ii) Line infiltration will be defined as extravasation of fluid into soft tissue around the region of the catheter tip.
- iii) Line occlusion will be defined as inability to infuse fluid, resulting in removal of line.
- iv) Phlebitis will be defined as presence of a linear red streak developing along the superficial veins from the catheter insertion site.
- v) Line associated thrombosis will be defined as ultrasound proven evidence of an occlusive thrombus in an anatomic location in proximity to the site of PICC.
- vi) CLABSI will be defined according to Center for Disease Control definitions, that is, (1) confirmed primary bloodstream infection with (2) one of following clinical signs of infection (fever, hypothermia, apnea, or bradycardia) and (3) presence of central catheter at the time of or within 48 hours before the onset of the infection.
- vii) Major life-threatening complications will include pleural effusion, pericardial effusion and cardiac tamponade, retroperitoneal extravasation etc

**6.2. Secondary outcome:** Secondary outcome will be time to complication post insertion. This will be defined as the interval between PICC line insertion and first detection of complication post insertion, expressed in days.

## 7. Statistical analysis:

### 7.1. Sample size calculation:

Based on our previous retrospective study, the rate of PICC complication resulting in removal of PICC was 30%. In order to find a clinically important difference of 10% between PICCs inserted through upper extremity and lower extremity, a sample of 153 infants in each group will be required at 80% power and alpha error of 5%. We will recruit 320 infants. . Approximately 200-250 PICCs are inserted per year in Calgary NICUs. We expect to complete recruitment over 18 month's period.

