### 3. Study hypothesis:

We hypothesize that there is an association between the site of PICC insertion and the complications necessitating PICC line removal non-electively and complications rates are different between upper extremity and lower extremity PICCs.

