#### 5.5. Randomization:

Eligible infants will be randomly assigned for upper extremity or lower extremity PICC insertion using an allocation ratio of 1:1. We will use blocked randomization of varying block sizes in multiples of two. The investigators will be blinded to the block sizes; but the block sizes will ensure appropriate balance between both arms. Infants will be stratified into two groups based on the gestational age ( $\leq 32$  weeks,  $>32$  weeks). Randomization will be performed using computer generated software once eligibility is confirmed and informed consent is obtained. A unique patient identification number and the randomisation sequence will be generated.

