**10. Feasibility and limitations:**

Major limitation of the study is the large sample size. We expect around 320 babies to be enrolled to see an effect. In our retrospective study, there were around 900 first time PICCs over a period of 5 years from 2006- 2010, which gives an average of 180-200 PICCs per year. Accordingly, it will take about 1.5-2 years to finish the trial.

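### 153 infants per group does not follow from the plan's own inputs: a two-arm comparison needs 294 to 356 per group, and 320 infants give about 47–54% power, not 80%

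*Combined protocol and SAP*

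**What the plan says.** Section 7.1 of the combined protocol and SAP gives the whole justification for the trial's size.

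- Baseline: in the earlier retrospective study "the rate of PICC complication resulting in removal of PICC was 30" per cent.
- Target difference: "In order to find a clinically important difference of 10% between PICCs inserted through upper extremity and lower extremity".
- Result: "a sample of 153 infants in each group will be required at 80% power and alpha error of 5" per cent.
- Target: "We will recruit 320 infants", that is 160 per arm. Section 10 repeats the number: "We expect around 320 babies to be enrolled to see an effect".

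Section 7.1 does not give the formula, the sidedness of the test, the direction of the 10%, or a dropout allowance.

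Other sections settle most of what is needed. Section 5.1 describes a parallel-group trial, and section 5.5 has infants "randomly assigned for upper extremity or lower extremity PICC insertion using an allocation ratio of 1:1". The hypothesis in section 3 is non-directional: "complications rates are different between upper extremity and lower extremity PICCs". Section 7.2 compares the two arms on a binary outcome by chi-squared or Fisher exact test at the 5% level.

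**The concern.** With rates near 30%, detecting a 10-point difference between two randomised groups with 80% power normally takes about 300 infants per arm or more. The stated 153 is roughly half that, which is what results if one arm's rate is treated as a known constant.

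The primary comparison rests on this figure. The rationale presents the trial as the way to settle whether site matters, and section 11 expects a significant difference to guide inserters. If true power is near 50%, a non-significant result is about as likely as a significant one even when the 10-point difference is real. Such a result could be misread as evidence that site makes no difference. The ethics board and parents would also be relying on a stated 80% that the plan's inputs do not support.

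**Working it through.** **Inputs.** From 7.1: rate 30%, difference 10% (read as percentage points), power 80% (z = 0.8416), alpha 5%. From 5.5: 1:1 allocation. The test is taken as two-sided (z = 1.96) because the hypothesis in section 3 is non-directional.

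**1. Reproducing 153.** The one-sample formula, with one group at p1 tested against a fixed p0, is

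n = [1.96·√(p0(1−p0)) + 0.8416·√(p1(1−p1))]² / (p1−p0)²

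With p0 = 0.30 and p1 = 0.20: [1.96·√0.21 + 0.8416·√0.16]² / 0.01 = (0.898 + 0.337)² / 0.01 = 152.5, rounded up to **153**. With p1 = 0.40 the same formula gives 172.

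**2. The two-arm requirement.** With p̄ the mean of the two rates,

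n per group = [1.96·√(2p̄(1−p̄)) + 0.8416·√(p1(1−p1) + p2(1−p2))]² / (p1−p2)²

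- 30% vs 20%: (1.2002 + 0.5119)² / 0.01 = 293.2, so **294** per group (588 in total).
- 30% vs 40%: (1.3221 + 0.5646)² / 0.01 = 355.9, so **356** per group (712 in total).
- 25% vs 35%, if 30% is the overall rate: **329** per group.

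**3. Other readings of the stated inputs.**

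| Reading | 30% vs 20% | 30% vs 40% |
|---|---|---|
| Two-sided, pooled | 294 | 356 |
| With continuity correction | 313 | 376 |
| Unpooled variance | 290.4 | 353.2 |
| Arcsine | 291.7 | 355.4 |
| One-sided | 231 | 281 |

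Reading 10% as relative gives 3,554 per group (30% vs 27%) or 3,763 (30% vs 33%). None of these is near 153.

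**4. Power actually available.** Power = Φ{[|p1−p2|·√n − 1.96·√(2p̄(1−p̄))] / √(p1(1−p1) + p2(1−p2))}

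At 160 per arm:

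- 30% vs 20%: Φ[(1.2649 − 1.2002) / 0.6083] = Φ(0.106) = **54.2%**
- 30% vs 40%: Φ[(1.2649 − 1.3221) / 0.6708] = Φ(−0.085) = **46.6%**

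At 153 per arm the figures are 52.4% and 45.0%. Exact binomial enumeration at 160 per arm gives 54.7% and 47.0% for the chi-squared test, and 49.3% and 42.5% for Fisher's test. Even one-sided at 5%, power at 160 per arm is only 66.4% and 59.2%.

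**5. Detectable difference.** Solving the power formula for 80% at 160 per arm gives a fall from 30% to about 16.8% (13 points) or a rise to about 45.1% (15 points).

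**6. Precision.** With both arms at 30%, the 95% confidence interval half-width for the risk difference is 1.96·√(2·0.3·0.7/160) = 0.100, that is 10.04 points. An observed difference of zero at that rate would just fail to exclude 10 points.

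**7. Crossover (illustration only).** Section 5.6 allows attempts in the non-designated region after two failed attempts, while 7.2 analyses by intention to treat. The plan gives no crossover rate. Assume a fraction c crosses each way and takes on the risk of the site actually used. The difference then becomes 10·(1 − 2c) points, and power at 160 per arm is:

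| c assumed | Difference (points) | From 30% vs 20% | From 30% vs 40% |
|---|---|---|---|
| 5% | 9 | 46% | 39% |
| 10% | 8 | 38% | 32% |
| 20% | 6 | 24% | 20% |

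**The case against.** The arithmetic was not disputed. The fair objections concern how far the surrounding statements reach.

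- **Origin of 153.** The plan names no formula or software. The one-sample match is exact but holds for one direction only, and different, unstated inputs could also give 153: a two-arm comparison of 6% vs 16% does. The origin is therefore an inference. The finding does not depend on it, because 153 is too small for the stated inputs whatever its source.
- **Assumed readings.** A two-sided test, percentage points, and 30% as one arm's rate are all assumptions. Each alternative was tried: one-sided needs 231 to 281 per group, relative 10% needs more than 3,500, and 25% vs 35% needs 329. None rescues 153.
- **Zero-difference statement.** This is close to the edge. At 25% in both arms the half-width is 9.5 points and at 20% it is 8.8, so a zero difference would then exclude 10 points. The statement holds at the plan's own 30%, and only just.
- **Crossover.** The rates are assumed and the conclusion does not need them.
- **Intervals already planned.** Section 7.2 does commit to event rates and a relative risk with 95% confidence interval. This deserves credit, but it does not correct the power claim, and the plan frames its target as an absolute difference.

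Nothing elsewhere in the plan offsets the shortfall. The interim look in 8.3 at p < 0.001 has negligible effect on sample size, and 320 exceeds 2 × 153 = 306 by only 14 infants.

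**Conclusion.** The concern holds. Section 7.1 is wrong as written: its inputs require 294 per group (30% vs 20%) to 356 per group (30% vs 40%), roughly 1.9 to 2.3 times the stated 153 (294/153 = 1.92; 356/153 = 2.33). The planned 320 infants give about 54% or 47% power for a 10-point difference, and somewhat less if Fisher's test is used. Power of 80% applies only to differences of about 13 points downward or 15 upward.

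These figures assume a two-sided 5% test, no continuity correction, 10 percentage points, equal arms, and no loss or crossover. Loss or crossover would lower power further. The error affects the primary outcome and must be corrected.

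**What to change.** Correct section 7.1, and section 10 where it relies on the same number:

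- State the method, the sidedness, both assumed rates, and that the 10% is absolute.
- State that 320 infants give about 54% (30% vs 20%) or 47% (30% vs 40%) power for a 10-point difference in a two-sided two-sample comparison.
- State that 80% power is reached only for differences of about 13 points downward or 15 points upward.
- State that 294 to 356 per group would be needed for 80% power at 10 points.
- In section 7.2, add the risk difference with its 95% confidence interval beside the relative risk. Commit to interpreting a non-significant primary result through that interval and not as evidence of no difference.

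If the sample stays at 320, the cost is protocol wording and a less favourable power statement, with no extra infants. Enlarging the trial to 588–712 infants is a separate decision for the investigators. At the 180–200 first-time PICCs per year given in section 10, that would take about 3 to 4 years (588/200 = 2.9; 712/180 = 4.0) even if every such infant were enrolled.

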## 7.2. Statistical methods:

Data will be analyzed using intention-to-treat analysis. Baseline demographics of the study population will be described using descriptive statistics. Data will be checked for normality. Categorical variables will be presented as counts and percentages and continuous variables as mean and standard deviation or median and inter-quartile range if data are not normally distributed. Primary outcome, which is the presence of any complication, necessitating PICC removal, is a binary outcome where we will use chi-squared test or Fisher exact test. Event rates, relative risk and 95% confidence intervals will be reported for primary outcome. Secondary outcome, which is the time from PICC insertion to development of complication, is a continuous outcome for which two sided independent samples t-test or Mann-Whitney U test, depending on if the data is normally distributed or not. Standard deviation and 95% confidence interval will be reported for continuous outcomes. We will also calculate time to complication post insertion as median time. We will also do multivariate logistic regression analysis to examine the association of PICC site and complication rate after adjusting for gestational age, day of PICC insertion and illness severity score. P-value <0.05 will be taken as significant. Stata 15 will be used for the analysis.

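### The primary chi-squared or Fisher test leaves out the gestational-age strata used in randomisation: valid, but conservative if complication risk differs between strata

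*Combined protocol and SAP*

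**What the plan says.** In the combined protocol and SAP, section 5.5 (Randomization) states: "Infants will be stratified into two groups based on the gestational age", with the cut at 32 weeks. It adds "We will use blocked randomization of varying block sizes in multiples of two" and says that "the block sizes will ensure appropriate balance between both arms".

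Section 7.2 (Statistical methods) says that the primary outcome "is a binary outcome where we will use chi-squared test or Fisher exact test". It continues: "Event rates, relative risk and 95% confidence intervals will be reported for primary outcome". The threshold is "P-value <0.05 will be taken as significant". No stratified test and no stratum-adjusted effect measure is named there or elsewhere.

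Later in section 7.2 comes a further analysis: "We will also do multivariate logistic regression analysis to examine the association of PICC site and complication rate after adjusting for gestational age", together with day of insertion and illness severity score. It is introduced as an addition to the primary test. The text does not say whether gestational age enters as the randomisation stratum.

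**The concern.** Blocking within strata makes the arms nearly identical in gestational-age mix, so differences in risk between strata contribute almost nothing to the sampling error of the treatment comparison. A pooled chi-squared test does not use this. Its variance, based on the overall proportion, still includes the between-stratum component and is too large whenever the strata differ in risk. The p-value then tends to be too large and the crude confidence interval too wide.

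What is at stake is precision, not validity. It matters somewhat more here because section 5.3 admits infants of all gestational ages, so risk may well differ across the 32-week cut, and because the trial has little power to spare (step 1 of the working).

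There is also a smaller reporting gap. Section 7.1 sizes the trial on a 10% difference (read here as absolute; the text does not say), but section 7.2 names only the relative risk. A crude risk difference can be derived from the planned event rates.

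**Working it through.** **Inputs from the documents.** Overall complication rate 30%, difference 10%, 80% power, alpha 5%, 153 per group, 320 recruited (section 7.1); 1:1 blocked allocation in two strata (section 5.5); threshold p < 0.05 (section 7.2).

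**Assumptions.** Stratum shares and stratum risks are not given, so ranges are shown. The 30% comes from a source whose title in the reference list describes preterm infants. Tests are two-sided, with 160 per arm and exact balance within strata.

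**1. The plan's own figure.** For 30% versus 20%, the two-sample formula gives

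n = [1.96·√(2·0.25·0.75) + 0.8416·√(0.21 + 0.16)]² / 0.10² = (1.2002 + 0.5119)² / 0.01 ≈ 293.2, so 294 per group.

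For 30% versus 40% it gives 356. The stated 153 does not reproduce as a two-group size. It matches a one-sample formula: (1.96·√0.21 + 0.8416·√0.16)² / 0.01 ≈ 152.5. At 160 per arm the normal approximation gives about 54% power for 30% versus 20%. That is a separate problem, but it sets the baseline for the comparisons below.

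**2. Share of variance lying between strata.** With w the share of the first stratum and g the gap in risk, r = w(1−w)g² / (0.3·0.7). For w = 0.5 and g = 0.20, r = 0.01/0.21 = 4.76%. Dropping the strata then costs the equivalent of 320·0.0476 ≈ 15 infants.

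**3. Actual type I error of the chi-squared test.** The true variance is (1−r) times the variance the test assumes, so alpha = 2·[1 − Φ(1.96/√(1−r))]. For r = 4.76%, 1.96/√0.9524 = 2.008, giving 4.46%.

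| Strata | Gap (points) | r | Infants out of 320 | Type I error |
|---|---|---|---|---|
| 50:50 | 10 | 1.2% | 4 | 4.9% |
| 50:50 | 20 | 4.8% | 15 | 4.5% |
| 50:50 | 30 | 10.7% | 34 | 3.8% |
| 80:20 | 10 | 0.8% | 2 | 4.9% |
| 80:20 | 20 | 3.0% | 10 | 4.7% |
| 80:20 | 30 | 6.9% | 22 | 4.2% |

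Simulation agrees to about 0.1 points. With no gap the chi-squared test is at about 5%. The CMH test stays at about 5% throughout.

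**4. Power at 30% versus 20% overall** (400,000 simulated trials per row, Monte Carlo standard error about 0.08 points; CMH without continuity correction). Pairs are the two arms' rates within a stratum.

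| Stratum 1; stratum 2 | Share | Chi-squared | CMH |
|---|---|---|---|
| 30/20; 30/20 | no gap | 54.8% | 54.3% |
| 35/25; 25/15 | 50:50 | 54.7% | 54.9% |
| 32/22; 22/12 | 80:20 | 54.7% | 54.6% |
| 36/24; 21/14 | 60:40 | 54.8% | 55.2% |
| 34/24; 14/4 | 80:20 | 54.8% | 55.8% |
| 40/30; 20/10 | 50:50 | 54.8% | 56.7% |
| 45/30; 15/10 | 50:50 | 55.0% | 58.2% |
| 45/35; 15/5 | 50:50 | 55.0% | 59.8% |

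The last row has a 30-point gap in both arms; the row above it has that gap in one arm only.

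**5. What a reader of the results would see.** The median chi-squared p-value is 0.039 in every case examined. For CMH it is 0.039 (no gap), 0.037 (10 points), 0.034 (20 points) and 0.031 (45/30; 15/10). The crude 95% half-width for the risk difference is 1.96·√(0.37/160) = 9.4 points. Stratified, for 40/30 and 20/10, it is 1.96·√[0.25·(0.24+0.21)/80 + 0.25·(0.16+0.09)/80] = 9.2 points.

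**6. If Fisher is chosen,** which section 7.2 also allows, power is about 49% and type I error about 3.7% even with no gap. Most of that loss comes from the Fisher test itself, not from ignoring the strata.

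**The case against.** The strongest reply is that nothing here can produce a false claim. The planned test is valid, any error is on the safe side, and a model adjusting for gestational age is already prespecified. The dispute is then only over which of two planned analyses is called primary, and the benefit depends on stratum risks that the documents do not supply. The background section links PICC use especially to very low-birth-weight infants, which suggests, without proving it, that the ≤32-week stratum will be the larger. In the 80:20 power scenarios above, the change is only −0.1 to +1.0 points. In a trial of 294 per arm the gain also shrinks, to 1.5 points for 40/30 and 20/10 and 0.9 for 34/24 and 14/4.

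Most of this stands as a limit on size. It does not remove the point. The logistic model is explicitly additional, carries two further covariates, is not tied to the randomisation stratum, and yields an odds ratio. The primary p-value and the reported relative risk therefore remain unstratified. The half-point cost of CMH when gestational age is not prognostic is real at 160 per arm, but it is not a general property: at 294 per arm both tests give 80.3%. The missing risk difference is rightly seen as secondary.

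**Conclusion.** The concern holds. The primary test omits the factor on which randomisation is stratified. It does not exceed its nominal level because of this, and it becomes conservative to the extent that risk differs between strata. The effect is close to nil for gaps of 10 points or less. With equal strata, the gain from stratifying is about 2 power points for a 20-point gap and 3 to 5 for a 30-point gap, depending on whether that gap is present in one arm or both. It is smaller if one stratum dominates. All of this assumes 30% overall risk, 160 per arm and illustrative stratum risks, and the documents do not show which case applies. The change is worth making as an efficiency refinement. It would not bring power from about 54% to the stated 80%.

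**What to change.** In section 7.2, name one primary test: a two-sided Cochran-Mantel-Haenszel test stratified by gestational age as randomised (≤32, >32 weeks). Report the stratum-adjusted relative risk and risk difference, each with a 95% confidence interval, alongside the planned event rates. The risk difference puts the result on the scale of the 10% target in section 7.1, read as absolute. Keep the crude chi-squared test as a sensitivity analysis. Naming a single test also closes the open choice between chi-squared and Fisher.

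The cost is SAP wording and a little analysis work, fixed before outcome data by arm are seen. The stratum is already recorded for randomisation, so no new data are needed. The downside is about half a point of power at 160 per arm (54.3% versus 54.8%) if gestational age turns out not to be prognostic.

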#### 5.6. Interventions:

PICC insertion attempts will be made by certified health care providers including transport nurses, nurse practitioners and physicians using standard clinical practice guidelines. A maximum of two attempts will be allowed in the designated region, following which further attempts will be considered in the non-designated region if the inserter is confident of success. Number of attempts at insertion and sites of attempts will be recorded as per unit protocol. After the catheter is inserted, catheter tip position will be confirmed by radiograph with the limbs in standard position as per unit protocol, and repeat radiographs will be taken if there is a manipulation. As per unit protocol, the catheter inserter will record the details of the procedure, the type of catheter used, and position of catheter following radiographic confirmation in the progress note of each infant's medical chart. Similarly, the bedside nurse also documents this information in the nursing chart/Metavision. In addition, the inserter will fill out a one-page PICC line tracking sheet for all the lines which includes details such as the indication, date of insertion, site of insertion, catheter tip position, and any complications during insertion. Once the

PICC is removed, the bedside nurse will complete the PICC tracking sheet, filling in the date and the reason for removal of the line.

The clinical goal is to place the catheter tip in the superior vena cava or inferior vena cava, but outside the right atrium. A catheter tip lying beyond the medial end of the clavicle and up to 1 cm at the junction of right atrium and superior vena cava is considered optimal for upper extremity. PICCs with the catheter tip located in the inferior vena cava below the diaphragm are considered optimal for lower extremity PICCs. Heparin will be infused in all PICCs as per standard unit policy. All catheters will be removed either after completion of intravenous therapy or earlier if they develop complications. In all babies an ultrasound will be performed within 72 hours of PICC line removal by neonatologists trained to perform point of care ultrasound, looking for the presence of an occlusive thrombus. If one is detected, consultation to radiology and hematology will be requested as per unit protocol.

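### The t-test or Mann-Whitney planned for time to complication uses only infants who had a complication, so it does not compare the randomised arms

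*Combined protocol and SAP*

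**What the plan says.** Time to complication is the only secondary outcome. Section 6.2 defines it as the "interval between PICC line insertion and first detection of complication post insertion, expressed in days". Section 7.2 treats it as continuous: it "is a continuous outcome for which two sided independent samples t-test or Mann-Whitney U test", the choice depending on normality, with p<0.05 taken as significant. The section adds: "We will also calculate time to complication post insertion as median time". It opens with the statement "Data will be analyzed using intention-to-treat analysis".

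Section 5.6 explains how observation ends: "All catheters will be removed either after completion of intravenous therapy or earlier if they develop complications". A line can therefore finish its course with no complication.

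The documents contain no censoring rule, no value or rank for infants without a complication, and no Kaplan-Meier, log-rank, Cox or competing-risk method. The multivariable logistic regression in Section 7.2 models whether a complication occurs, not when.

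**The concern.** Under the Section 6.2 definition, an infant without a complication has no time to complication. With no rule for such infants, the t-test or Mann-Whitney can be run only on those who had one. The two groups are then subsets selected by an event after randomisation, so randomisation no longer protects the comparison, and the intention-to-treat commitment cannot be met for this outcome.

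The question also changes. The test asks whether complications, once they have happened, happened earlier in one arm. A clinician will want to know whether lines at one site fail sooner across all infants assigned to that site. A site with twice as many complications but the same timing among them would show no difference. A site whose extra complications come late would appear to have a longer time to complication, which reads as a benefit.

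The reported median has the same ambiguity. It could be a Kaplan-Meier median over all infants or a simple median among infants with a complication, and these are different quantities.

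**Working it through.** The documents give no power, event count or other figure for the secondary outcome, so there is no figure of the plan's to reproduce.

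**Inputs from the documents**
- 320 infants, 1:1 allocation, so 160 per arm (Sections 7.1, 5.5).
- Complication rate 30%, difference of interest 10%, read as percentage points (Section 7.1).
- Literature range 27–42% (Section 1.1).
- Two-sided test at 5% (Section 7.2).

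**Step 1: who enters the test.** Contributors = 160 × p₁ + 160 × p₂.

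| Rates in the two arms | Contributors of 320 |
|---|---|
| 30% and 30% | 48 + 48 = 96 (30%) |
| 30% and 20% | 48 + 32 = 80 (25%) |
| 30% and 40% | 48 + 64 = 112 (35%) |
| 27% overall | 320 × 0.27 = 86 |
| 42% overall | 320 × 0.42 = 134 |

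At 30%, 320 − 96 = 224 randomised infants contribute nothing. The 30% counts complications leading to removal. If Section 6.2 also covers complications without removal the share could be higher, but no figure is given.

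**Step 2: why the test barely sees a difference in hazard.** Assume exponential times with a mean of 20 days to elective removal. A complication risk p then needs a complication hazard of (p/(1−p))/20. The time among infants with a complication is exponential with rate (p/(1−p))/20 + 1/20 = 1/(20(1−p)), so its mean is 20(1−p). That is 14 days at p = 0.30 and 16 days at p = 0.20. The two hazards are 0.0214 and 0.0125 per day, a ratio of 0.58, yet the mean times among complicated infants differ by only 2 days. With 4,000 simulated trials on these assumptions, Mann-Whitney is significant in 8% and log-rank on all infants in 65%.

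**Step 3: base simulation.** 160 per arm, 3,000 trials, constant complication hazards solved to give the stated risks, and lognormal time to elective removal (median 12 days, log-scale SD 0.6). All timing inputs are assumptions. Mann-Whitney uses complication times only; the log-rank test is unstratified and censors elective removal; chi-squared has no continuity correction.

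| True risks | Mann-Whitney | Log-rank, all infants | Primary chi-squared |
|---|---|---|---|
| 30% / 30% | 4.9% | 4.5% | 4.8% |
| 30% / 20% | 5.8% | 58% | 54% |
| 40% / 30% | 7.2% | 54% | 48% |
| 30% / 15% | 6.9% | 93% | 91% |
| 42% / 27% | 10.7% | 87% | 81% |

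At 30% / 20% the t-test is significant in 6.8%. Varying the median dwell (8 or 20 days), its SD (0.3 or 0.9) or the Weibull shape of the complication hazard (0.7 or 1.5) gives Mann-Whitney 6–8% and log-rank 55–66%. An independent rerun of the base case agrees within simulation error.

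The log-rank figure can be checked approximately by the Schoenfeld formula. The hazard ratio is ln(0.80)/ln(0.70) = 0.63 with 80 events, so power = Φ(0.469 × √80/2 − 1.96) = Φ(0.138) = 55%.

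**Step 4: can it mislead?** In the base case Mann-Whitney is significant in the wrong direction in 1.2% of trials (0.4–1.8% over the sensitivity range). Two constructed scenarios show when this becomes material:
- *Late excess.* Both arms have 20% early complications (uniform on days 1–7) and one arm has 10 points more. If all the excess is late (uniform on days 8–20), Mann-Whitney significantly favours the worse arm in 73% of trials. If half is late, 22%.
- *Unequal dwell.* Complication hazards are equal, but mean time to elective removal is 20 days in one arm and 10 in the other. Mann-Whitney is significant in 47% of trials and log-rank in 5%.

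**Step 5: the median.** At 30% / 20% in the base case, a Kaplan-Meier median with elective removal censored is reached in 89% of trials in the 30% arm and 54% in the 20% arm. With SD 0.3 these fall to 40% and 15%. A Kaplan-Meier median may therefore not exist in one or both arms.

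**The case against.** The strongest reply is that the power contrast is partly built in. With constant hazards and the same dwell distribution in both arms, timing among complicated infants hardly differs, so a rejection rate near 5% is bound to follow. The log-rank test does well largely because it picks up the same rate difference as the primary chi-squared. This stands as a description of the simulation: no information on complication rates is lost from the trial as a whole. It does not rescue the planned test, which still answers a question about a selected subset.

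The 73% is a worst case, with non-overlapping windows and the whole excess late. That is right. Milder versions give smaller figures, and nothing in the documents indicates timing by site.

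A rank test could include everyone if uncomplicated infants were given a rank. True, but the plan states no such rule, and elective removal at varying times makes one hard to define. Likewise, the median may be intended as Kaplan-Meier, but the named hypothesis test would still be the t-test or Mann-Whitney.

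The ambiguity about the event may be small, since Section 5.6 has lines removed when complications develop. This is fair. The clearest exception is thrombus found after removal, whose frequency is not given.

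Finally, the outcome is secondary, and the hypothesis and objective concern rates. That limits the weight of the point without removing it.

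**Conclusion.** The concern holds and should be fixed. As written, the test of the only secondary outcome uses about 30% of the randomised infants (25–35% under the plan's own 10-point difference), selected by an event after randomisation, and so conflicts with the promised intention-to-treat analysis. This follows from the definition and the named test, and needs no simulation.

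The size of the consequence does rest on assumed hazards and dwell times. Over the ranges tried at 30% versus 20%, the planned test rejects in 6–8% of trials, little more than its 5% error rate. A significant result favouring the worse arm is rare in the base case and becomes common only if the excess complications come late, which the documents neither support nor exclude.

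The trial's main conclusion, from the chi-squared analysis of all infants, does not depend on this test. The chi-squared power of about 54% in the table, against the planned 80%, is a separate sample-size matter.

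**What to change.** In Section 7.2, replace the t-test or Mann-Whitney with a time-to-event comparison by randomised arm: a log-rank test or cause-specific Cox hazard ratio, stratified by the two gestational-age groups used in randomisation. Censor at elective removal, and at death or transfer with the line in place. Show cumulative incidence curves by arm alongside, with those same events treated as competing.

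Then settle the following:
- **Median.** State that it is a Kaplan-Meier estimate, which may not be reached, or label it descriptive among infants with a complication.
- **Event and date.** Align Sections 6.2 and 7.2 on whether the event is first detection or a complication leading to removal, and which date is used.
- **Thrombus.** Section 5.6 says "In all babies an ultrasound will be performed within 72 hours of PICC line removal". State how a thrombus found then is timed, or report it by arm as a separate count.
- **Crossover and no line.** After two failed attempts, "further attempts will be considered in the non-designated region if the inserter is confident of success". State that these infants stay in their randomised arm. Report by arm how many never received a PICC, since they have no insertion date to start the clock.

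The cost is text edits only, with no change to sample size or procedures. If the event is a complication leading to removal, the data are already planned: the tracking sheet holds the insertion date, and the nurse completes it at removal, "filling in the date and the reason for removal of the line". If first detection is kept, that date must come from the chart, because the tracking sheet is not said to record it.
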